11.5.1.3 Handling of Missing Values/Censoring/Discontinuations

Any patients with missing information regarding response to treatment will be counted as non-responders.

11.5.2 Secondary Efficacy Objective

The secondary efficacy objectives and endpoints in the dose expansion part are (besides the ORR that is primary endpoint) those that are described in Section 11.4.4.

11.5.3 Secondary Safety Objective

The safety objective with the expansion part is to further describe the safety profile of GEN1029. AEs and laboratory parameters will be reported as described in 11.4.1 and 11.4.2. All listings and tables will be presented by cohort in the expansion part.

11.5.4 Pharmacokinetics

PK parameters will be calculated as feasible, depending on the availability of the data.

11.5.5 Immunogenicity of GEN1029

Immunogenicity of GEN1029 in the expansion part will be reported as described in Section 11.4.4. The association between positive/non-positive ADA and PK (pre-dose, AUC, Cmax), major safety signals (CTCAE \geq grade 3) and efficacy information (change in tumor size by CT scan) will be explored and reported as feasible.

11.6 Explorative Analysis

11.6.1 Biomarkers

Biomarker analyses in this study are exploratory and focused on identifying potential pharmacodynamic (PD) or predictive markers that may be further validated in prospective trials with GEN1029 (HexaBody-DR5/DR5), as well as to further understand the biological impact of GEN1029 on downstream pathway activities and tumor cell processes.

Biomarkers, such as DR5 expression (protein or) and immune cell populations, will be tabulated for all patients who had samples collected and testing performed. Biomarker assessments will be summarized by time point using descriptive statistics. Changes in biomarker parameters, as compared to baseline, will be calculated and analyzed for association with relevant clinical endpoints such as objectives response, PFS, OS. Subgroup analysis may be performed to evaluate differences between biomarker parameters in groups of responders and non-responders or other clinically relevant subgroups, and to evaluate the associations between biomarker parameters and specific clinical endpoints. Univariate and multivariate analyses, as well as pathway analyses may also be performed if applicable. Any pharmacodynamic measures will be listed, tabulated, and plotted as appropriate. Patients may be grouped by cohort, regimen, or clinical response.

Results of biomarker analyses may be presented in a separate report. Planned analyses are based on the availability of clinically valid assays and may be deferred if emerging study data show no likelihood of providing useful scientific information.

11.6.2 Metabolic Response in the Tumors

As an exploratory analysis the metabolic response in the tumors will be evaluated following the Positron Emission Tomography Response Criteria In Solid Tumors (PERCIST 1.0), see (Wahl et al., 2009). The metabolic endpoint is the standardized uptake volume corrected for body lean mass (SUL). Percentage change from screening in SUL will be summarized by scan visit for the hottest lesion. The metabolic response will also be classified and summarized (according to PERCIST 1.0) as a) complete metabolic response (CMR); b) partial metabolic response (PMR); c) stable metabolic disease (SMD); and d) progressive metabolic disease (PMD).

11.6.3

11.7 Interim Analyses

In the expansion part each cohort will contain of up to 4 stages, targeting a maximum sample size of 60 patients. For each stage, the success of the stage is predicted. If the predictive probability of success is less than 10% the stage is not further explored in order not to expose patients to inefficacious doses based on an interim futility analysis, as detailed in Table 11-3 and Table 11-7. The interim analysis divides each cohort into a maximum of 4 stages in total. The analysis will be based on both the uncomfirmed and confirmed CR or PR observed when the interim-sample size is accomplished.

Stage	Sample size at interim	Sample size at end of stage
	(n)	(N)
1	Not applicable	10
2	10	20
3	20	40
4	40	60

Table 11-3: Cohort stages and Sample Sizes

At the interim, a Bayesian predictive probability approach will be used to evaluate the futility criteria (Lee and Liu, 2008). By using predictive probabilities, it is possible to directly assess the outcome of a trial (in this case stage), if continued to its end (Saville et al., 2014). Given the interim data, the predicted probability is a *weighted average* of posterior probabilities, as if calculated given the outcome at the end of the stage. The weights correspond to how likely each outcome is. The predictive probabilities may in fact be calculated at any time point during Stage 2, 3 and 4.

As originally suggested by Lee and Liu (Lee and Liu, 2008) the predictive probability approach is operated with respect to a historical response rate (p_0) only. However, as applied here, also a target response rate (p_1) that warrants further evaluation of the drug, is being used to evaluate futility. In general, this decreases the Type I error rate and increases the Type II error rate as more studies would be stopped. For more details, please see Section 11.8.2.

For Stage 2, the success criteria for each cohort is a posterior density (given completion of stage) of the responder rate that exceeds p_0 by **set of** and p_1 by **set of**. Stage 2 is further explored if the predictive probability of success, as calculated at end of Stage 1, is greater than **set of**. Similar considerations yield for Stage 3 and 4, but the success criteria are a posterior density of the responder rate that exceeds p_0 by **set of** and p_1 by **set of**. The success criteria based on the posterior probabilities are illustrated in Figure 11-1, where the more conservative expansion strategy being used for Stage 3 and 4 as compared to Stage 2 becomes clear.

Figure 11-1: Success criteria based on posterior probabilities

In addition to the interim analysis for futility, interim data from the trial may be presented at scientific meetings.

The Statistical Analysis Plan will describe the planned interim analyses in greater detail.

11.8 Sample Size Calculation

11.8.1 Dose Escalation Part

The actual number of patients depends on the true relationship between dose and DLT probability and could range between 10 to 25 patients for a given scenario, as presented below. Similarly, the number of dose levels explored depends on the toxicity profile. Up to 18 additional patients may be recruited to dose levels below MTD where it is found relevant to further explore the efficacy.

In total up to approximately 100 patients are planned to be recruited during the escalation part. The patients are shared between the Biweekly and Priming Regimens.

Table 11-4 below shows 6 different scenarios for the probability of a patient having a DLT at 6 dose levels, which in our case could be the 6 lowest dose levels. For each scenario the total expected number of patients, when following the mBOIN design, is shown in the rightmost column. For each of the dose levels and scenarios, first the probability of a DLT and then the expected number of patients at the dose level is shown. The mBOIN design algorithm behaves as intended with most patients exposed to the dose levels with DLT probability close to the target DLT rate and fewer patients exposed in total if the toxicity is high at the lowest dose levels.

		Probability(DLT) and expected number of patients at dose level											
Scenario		Dose = 1	Dose = 2	Dose = 3	Dose = 4	Dose = 5	Dose = 6	No. Pat.					
1	Pr(DLT)	0%	1%	2%	4%	8%	16%						
	No. Pat.	1.0	3.1	3.2	3.5	4.2	8.7	23.8					
2	Pr(DLT)	1%	2%	4%	8%	16%	32%						
	No. Pat.	1.1	3.2	3.5	4.2	6.2	7.2	25.3					
3	Pr(DLT)	5%	15%	25%	40%	50%	60%						
	No. Pat.	1.8	5.6	6.5	4.6	1.5	0.2	20.2					
4	Pr(DLT)	20%	35%	50%	60%	65%	70%						
	No. Pat.	4.9	6.8	2.7	0.4	0.0	0.0	14.9					
5	Pr(DLT)	30%	40%	50%	60%	70%	75%						
	No. Pat.	5.4	5.5	1.8	0.3	0.0	0.0	13.0					
6	Pr(DLT)	1%	1%	1%	60%	65%	70%						
	No. Pat.	1.0	3.1	8.3	6.7	0.4	0.0	19.6					

 Table 11-4
 Modified BOIN Design Characteristics for 6 Dose Levels

If 4 dose levels are explored the pattern identified repeats, but the total number of patients is lower, see Table 11-5.

		Probability (DLT) and expected number of patients* at dose level									
Scenario		Dose = 1	Dose = 2	Dose = 3	Dose = 4	No. Pat.					
1	Pr(DLT)	2%	4%	8%	16%						
	No. Pat.	3.2	3.5	4.2	8.6	19.5					
2	Pr(DLT)	4%	8%	16%	32%						
	No. Pat.	3.4	4.2	6.1	6.9	20.6					
3	Pr(DLT)	15%	25%	40%	50%						
	No. Pat.	5.2	6.4	4.3	1.3	17.3					
4	Pr(DLT)	35%	50%	60%	65%						
	No. Pat.	6.4	2.9	0.5	0.0	9.9					
5	Pr(DLT)	40%	50%	60%	70%						
	No. Pat.	6.0	2.3	0.4	0.0	8.7					
6	Pr(DLT)	1%	60%	65%	70%						
	No. Pat.	8.3	6.6	0.4	0.0	15.4					

Table 11-5: Modified BOIN Design Characteristics for 4 Dose Levels

* Based on 50,000 simulations

11.8.2 Expansion Cohorts

The maximum sample size for each expansion cohort is 60 patients, divided over up to 4 stages as described in Section 11.7. The historical (p_0) and target (p_1) response rates being used to evaluate the operating characteristics are presented in Table 11-6.

	Colorectal Cancer (CRC)	Triple Negative Breast Cancer (TNBC)	Other indications*	
Historical response rate (p ₀)	2%	7.5%	10%	
Target response rate that warrants further evaluation of the drug (p ₁)	15%	20%	25%	
the drug (pl)				

Table 11-6: Response Rate Characteristics by Indication

*NSCLC, RCC, gastric, pancreas or urothelial cancer

Given p_0 and p_1 it is possible to prospectively calculate the required number of responders to further explore each stage as presented in Table 11-7. A priori it is assumed that the response rate is distributed as Beta(0.2, 0.8).

Table 11-7: Cont	tinuation Criteri	a in Terms of	Number of 1	Responders
------------------	-------------------	---------------	-------------	------------

Indication	Stage 2 (n=10; N=20)	Stage 3 (n=20; N=40)	Stage 4 (n=40; N=60)
CRC	≥1/10	≥2/20	≥4/40
TNBC	≥1/10	≥2/20	≥6/40
Other	≥1/10	≥3/20	≥7/40

Numbers of responses serve as a guideline; however, the totality of efficacy data will be considered when making decisions to terminate or continue an arm.

The operating characteristics in terms of the probability for not exploring a stage, and the probability that the estimated response rate is greater than p_1 (if the stage is completed) are presented in Table 11-8. The operating characteristics are based on 50,000 simulations of each assumption of true response rate. For the colorectal cohort there is a high probability to stop under p_0 early on, which partly is due to the requirement to beat p_1 (15%) with some confidence as well. This requirement has less impact on the TNBC cohort and the other indications (NSCLC, RCC, gastric, pancreatic and urothelial cancer) for which the stopping rate is lower.

Table	11-8	: Opera	ting C	Charac	teristics	in	Terms	of a)	Prob	ability	for 1	not E	Explor	ing	each
Stage;	and	b) the	Proba	bility 1	that the	Est	imated	Resp	onse	Rate is	Gre	ater	than	p1 (i	f the
Stage	is Co	mpleted	l)												

Indication	True ORR	Stage 2		Stage 3		Stage 4	
		(n=10; N=20)		(n=20; N=40)		(n=40; N=60)	
		a)	b)	a)	b)	a)	b)
CRC	2%	81%	1%	94%	0%	99%	0%
(p ₀ =2%; p ₁ =15%)	15%	20%	56%	18%	54%	13%	55%
TNBC	7.5%	46%	6%	55%	1%	92%	0%
$(p_0=7.5\%; p_1=20\%)$	20%	11%	58%	7%	56%	16%	54%
Other*	10%	35%	4%	68%	1%	90%	0%
(p ₀ =10%; p ₁ =25%)	25%	6%	58%	9%	55%	10%	54%

*NSCLC, RCC, gastric, pancreas or urothelial cancer

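### Table 11-8 column (a) treats each futility look in isolation, so the chance of dropping an active regimen before stage 4 is understated by up to 17 percentage points

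*Protocol*

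**What the plan says.** Section 11.7 of the protocol sets up a sequential design: "In the expansion part each cohort will contain of up to 4 stages, targeting a maximum sample size of 60 patients". The looks fall at 10, 20 and 40 patients, and the stages end at 20, 40 and 60 (Table 11-3). The stopping rule is that "If the predictive probability of success is less than 10% the stage is not further explored". Section 4.4 likewise describes patients as allocated stage by stage.

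Table 11-7 turns the rule into minimum numbers of responders at the three looks:

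- "CRC ≥1/10 ≥2/20 ≥4/40"
- "TNBC ≥1/10 ≥2/20 ≥6/40"
- "Other ≥1/10 ≥3/20 ≥7/40"

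Column (a) of Table 11-8 is introduced in Section 11.8.2 as "The operating characteristics in terms of the probability for not exploring a stage". Of its derivation the protocol says: "The operating characteristics are based on 50,000 simulations of each assumption of true response rate". Neither the title nor the text says whether column (a) is cumulative, conditional on reaching the look, or computed for each look alone. Section 11.7 notes that adding the target rate to the rule raises the Type II error rate, and sends the reader to Section 11.8.2 for the detail.

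**The concern.** At the target rate, the colorectal entries in column (a) run 20%, 18%, 13%. In a sequential design a cohort that does not explore stage 2 cannot explore stage 3 or 4, so the probability of not exploring a stage can only stay level or rise. The triple negative breast cancer row has the same fault, at 11%, 7%, 16%.

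Column (a) at the target rate is the only place where the plan states how often the futility rule would drop a regimen worth pursuing. The sponsor safety committee decides on further recruitment (Section 4.4). If it read the stage 4 entry as the chance of missing stage 4, it would take the rule to be safer for an active regimen than it is.

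**Working it through.** **Inputs.** Looks at n = 10, 20, 40 (Table 11-3). Minimum responders r: colorectal (CRC) 1, 2, 4; triple negative breast (TNBC) 1, 2, 6; other indications 1, 3, 7 (Table 11-7). Historical rate p0 and target rate p1: CRC 2% and 15%; TNBC 7.5% and 20%; other 10% and 25% (Table 11-6). The redacted posterior thresholds are not needed, because Table 11-7 prints the counts.

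**Step 1: reproduce the printed figures.** Take each look alone: P(X < r), with X binomial(n, p). For CRC at 15%:

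- n = 10: 0.85^10 = 19.7%
- n = 20: 0.85^20 + 20 × 0.15 × 0.85^19 = 3.9% + 13.7% = 17.6%
- n = 40: P(X ≤ 3) = 13.0%

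All rows, in % for stages 2 / 3 / 4:

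| Cohort, true rate | Printed (a) | Each look alone |
|---|---|---|
| CRC 2% | 81 / 94 / 99 | 81.7 / 94.0 / 99.2 |
| CRC 15% | 20 / 18 / 13 | 19.7 / 17.6 / 13.0 |
| TNBC 7.5% | 46 / 55 / 92 | 45.9 / 55.1 / 92.4 |
| TNBC 20% | 11 / 7 / 16 | 10.7 / 6.9 / 16.1 |
| Other 10% | 35 / 68 / 90 | 34.9 / 67.7 / 90.0 |
| Other 25% | 6 / 9 / 10 | 5.6 / 9.1 / 9.6 |

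All 18 cells agree within 1 point.

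**Step 2: follow a cohort through the looks.** The probability of not exploring a stage is the sum of the probabilities of a first stop at each look up to that stage. For CRC at 15%:

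- First stop at 10: 19.7%.
- First stop at 20: exactly 1 responder in the first 10 and none in the next 10, which is 10 × 0.15 × 0.85^9 × 0.85^10 = 0.347 × 0.197 = 6.8%.
- First stop at 40: 2 or 3 responders at 20 with at least one in the first 10, and at most 3 in total at 40. P(2 at 20, first look passed) = 0.2293 × (1 − 45/190) = 0.1750. P(3 at 20, first look passed) = 0.2428 × (1 − 120/1140) = 0.2173. The next 20 patients must then give at most 1 responder (0.1756) or none (0.0388): 0.1750 × 0.1756 + 0.2173 × 0.0388 = 3.9%.

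The cumulative values are 19.7%, 19.7 + 6.8 = 26.5%, and 26.5 + 3.9 = 30.4%.

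The same enumeration for every row (%, stages 2 / 3 / 4):

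| Cohort, true rate | Cumulative | Conditional on reaching the look | Stage 4: cumulative minus printed |
|---|---|---|---|
| CRC 2% | 81.7 / 95.3 / 99.5 | 81.7 / 74.5 / 89.5 | 0.5 |
| CRC 15% | 19.7 / 26.5 / 30.4 | 19.7 / 8.5 / 5.3 | 17.4 |
| TNBC 7.5% | 45.9 / 62.9 / 93.7 | 45.9 / 31.5 / 82.9 | 1.7 |
| TNBC 20% | 10.7 / 13.6 / 23.3 | 10.7 / 3.2 / 11.3 | 7.3 |
| Other 10% | 34.9 / 70.1 / 92.0 | 34.9 / 54.2 / 73.3 | 2.0 |
| Other 25% | 5.6 / 11.8 / 16.7 | 5.6 / 6.5 / 5.5 | 6.7 |

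Neither the cumulative nor the conditional reading fits the printed column beyond stage 2.

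**Step 3: cross-check with column (b).** The probability of passing only that stage's own look and finishing with an observed rate of at least p1 is, at p1, 56.0 / 54.2 / 54.9% for CRC, 57.6 / 55.7 / 54.2% for TNBC and 58.1 / 55.3 / 54.7% for other. The printed values are 56/54/55, 58/56/54 and 58/55/54. Requiring all earlier looks to be passed as well would give 56.0 / 49.9 / 47.1% for CRC. Stops at earlier looks were evidently not carried forward in either column.

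**The case against.** The strongest reply is that nothing was miscalculated. Each cell is a correct per-look probability, Section 11.7 speaks throughout of predicting the success of each stage, column (b) follows the same convention, and the table never uses the words cumulative or Type II. A falling sequence also shows an attentive reader that the column is not cumulative. On this view only a label and one overall figure are missing.

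That explains how the figures arose, but it does not rescue them. Stage 4 goes unexplored whenever any of the three looks fails, and for CRC at 15% that probability is 30%, not 13%. Nor is the printed value the probability of stopping at that look given that it is reached, which is 5%.

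Other points on that side stand as limits:

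- The 17 points is the CRC maximum. The gap is about 7 points for TNBC and for the other five indications.
- A reader who took the largest CRC entry, 20%, as the overall risk would be about 10 points short.
- At p0 the stage 4 gap is about 2 points at most.
- The counts are a guideline, so actual stopping could differ. Table 11-8, however, matches strict use of the counts look by look, so the guideline wording does not account for the difference.
- The expansion part was not initiated (SAP Section 3), so no cohort was stopped under this rule.

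**Conclusion.** The concern holds. Column (a) of Table 11-8 gives stand-alone probabilities for each look under a title that, in a sequential design, describes something else. At the target rate the probability of not exploring stage 4 is 30% for CRC, 23% for TNBC and 17% for the other indications, against 13%, 16% and 10% printed. For stage 3 it is 27%, 14% and 12%, against 18%, 7% and 9%. At the historical rate the main discrepancy is TNBC at stage 3, 63% against 55%; there the table understates how well the rule stops an inactive regimen.

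These figures assume that the Table 11-7 counts are applied strictly at all three looks and that responses are independent with a constant rate. The error lies in a stated design property and affects no reported result. It should still be corrected, because the table is the protocol's only account of the false-stop risk.

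**What to change.** Replace column (a) with cumulative probabilities and say so in the title (%, stages 2 / 3 / 4):

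| Cohort | At p0 | At p1 |
|---|---|---|
| CRC | 82 / 95 / 99.5 | 20 / 27 / 30 |
| TNBC | 46 / 63 / 94 | 11 / 14 / 23 |
| Other | 35 / 70 / 92 | 6 / 12 / 17 |

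Re-derive column (b) over the same path so that the table does not mix two bases. At p1 it becomes about 56/50/47 for CRC, 58/53/51 for TNBC and 58/54/52 for other; at p0 it moves by less than 0.1 point.

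Alternatively, label column (a) as conditional on reaching the look, print the conditional values from the working, and add the cumulative stage 4 figure. At the very least, the present column should be labelled as each look taken alone, with the cumulative figures beside it.

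The cost is one restated table and a less favourable stated stopping risk. The looks, the counts and the sample sizes stay as they are. Since the expansion was not opened, the correction matters for the record and for any later trial that reuses this design.

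### Protocol Table 11-8, column (b), is captioned as the chance of exceeding p1 once a stage is completed, but the printed values are the joint chance of passing that stage's own look and reaching at least p1

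*Protocol*

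**What the plan says.** Protocol section 11.8.2 defines two operating characteristics for each expansion stage. Column (a) is the probability that the stage is not explored. Column (b) is introduced with the words "the probability that the estimated response rate is greater than p_1 (if the stage is completed) are presented in Table 11-8", and the table title repeats that definition. The operative phrase, "the probability that the estimated response rate is greater than" p1, states a strict inequality.

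Each stage is headed by one interim size and one final size, for example "Stage 2 (n=10; N=20") for Stage 2. Table 11-7 gives the responder counts needed to continue: "CRC ≥1/10 ≥2/20 ≥4/40"; "TNBC ≥1/10 ≥2/20 ≥6/40"; "Other ≥1/10 ≥3/20 ≥7/40". On precision, the section states that "The operating characteristics are based on 50,000 simulations of each assumption of true response rate".

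Neither the text nor the title says that column (b) is joint with passing the look, that an estimate exactly equal to p1 counts, or that each stage is evaluated with its own look alone.

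**The concern.** The ordinary reading of the caption is a conditional probability with a strict inequality: among completed stages, how often does the estimate exceed the target? On that reading, a colleague would take 54 to 58% as the chance that a completed stage beats the target when the true ORR equals the target.

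The same reader might multiply by the chance of completing the stage. For CRC at 15%, Stage 2, that would be 0.80 × 56% = 45%. If 56% already includes passing the look, this applies the look twice.

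The inequality matters as well. The product p1 × N is a whole number at every stage, so a sizeable probability sits exactly on p1, and counting it or leaving it out moves the answer by more than ten points.

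**Working it through.** **Inputs** (Protocol Tables 11-6, 11-7 and 11-8)
- p0: CRC 2%, TNBC 7.5%, Other 10%. p1: 15%, 20%, 25%.
- Interim n and final N: 10/20, 20/40, 40/60.
- Minimum responders r at each look: CRC 1, 2, 4; TNBC 1, 2, 6; Other 1, 3, 7.
- t = p1 × N: CRC 3, 6, 9; TNBC 4, 8, 12; Other 5, 10, 15.

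**Formulas**, with X binomial at the true ORR:
- Column (a): P(X_n < r).
- Joint, at least p1: J≥ = P(X_n ≥ r and X_N ≥ t).
- Joint, strictly above p1: J> = P(X_n ≥ r and X_N > t).
- Conditional on passing that look: divide by P(X_n ≥ r).

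**Worked cell: CRC, true ORR 15%, Stage 2**
1. P(X_10 = 0) = 0.85^10 = 0.1969. This is column (a), printed as 20%.
2. P(X_20 ≥ 3) = 0.5951 with no look applied.
3. The part lost at the look is 0.1969 × P(Bin(10, 0.15) ≥ 3) = 0.1969 × 0.1798 = 0.0354.
4. J≥ = 0.5951 − 0.0354 = 0.5597. The table prints 56%.
5. P(look passed and X_20 exactly 3) = 0.2173, so J> = 0.5597 − 0.2173 = 0.3424.
6. Given that the look is passed, strictly above: 0.3424 / 0.8031 = 42.6%.

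**All cells at true ORR = p1, Stages 2/3/4 (%)**

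| Quantity | CRC | TNBC | Other |
|---|---|---|---|
| Printed (b) | 56/54/55 | 58/56/54 | 58/55/54 |
| Joint, ≥ p1, own look only | 56.0/54.2/54.9 | 57.6/55.7/54.2 | 58.1/55.3/54.7 |
| Conditional on own look, > p1 (as captioned) | 42.6/46.5/47.2 | 41.1/43.5/50.1 | 40.4/45.5/47.6 |
| Joint, > p1, own look only | 34.2/38.3/41.0 | 36.7/40.5/42.0 | 38.2/41.3/43.0 |
| Conditional on own look, ≥ p1 | 69.7/65.7/63.1 | 64.5/59.9/64.7 | 61.5/60.8/60.5 |

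**At true ORR = p0**, the joint ≥ values are CRC 0.64/0.01/0.00 (printed 1/0/0), TNBC 5.61/0.86/0.14 (printed 6/1/0) and Other 4.26/0.49/0.07 (printed 4/1/0).

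All 18 cells of column (b) agree with the joint, own-look, ≥ p1 definition within 0.7 point. All 18 cells of column (a) agree with the own-look stopping probability within 0.75 point. With 50,000 simulations the Monte Carlo standard error near 55% is √(0.55 × 0.45 / 50,000) = 0.22 point. The few cells that differ by a rounding step, such as Other Stage 4 (54.7 against 54), are compatible with that.

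**Other definitions tried, none of which fits**
- Joint ≥ p1 with no look: CRC Stage 2 is 59.5 against 56.
- Joint ≥ p1 after surviving all earlier looks: CRC Stages 3 and 4 are 49.9 and 47.1 against 54 and 55.
- Joint with the posterior mean strictly above p1, using the stated prior ("A priori it is assumed that the response rate is distributed as Beta(0.2, 0.8")): Stage 2 gives 36.7 for TNBC and 38.2 for Other, against 58 for each.

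**The case against.** The strongest reply is that nothing was miscalculated and the caption is only loose. The parenthesis about completion never says that the probability is taken among completed stages. Beside column (a), it can be read as *the stage is completed and the estimate reaches target*. The outcomes then partition neatly: for CRC at 15%, Stage 2, 20% are not explored, 56% are completed at or above target, and the remaining 24% are completed below it.

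That reply stands in part. The simulation did compute a coherent quantity, and the joint reading of the parenthesis is possible. It does not rescue the caption: the joint probability of being strictly greater than p1 is 34 to 43%, which is 11 to 22 points below print.

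A reader might also infer that the captioned quantity conditions on surviving every look up to that stage, which for CRC would give about 49% and 52% at Stages 3 and 4. The documents do not support that. Each column is headed by one look and one final size, column (a) is also computed look by look, and nothing in the caption mentions earlier looks.

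Finally, nothing identified depends on column (b). Continuation rests on predictive probability and the counts in Table 11-7, which the protocol calls a guideline. With one regimen per indication, the ORR analysis is estimation only.

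**Conclusion.** The concern holds as a misdescribed operating characteristic. At a true ORR equal to p1, column (b) prints 54 to 58%, where the captioned quantity is 40 to 50%, a gap of about 4 to 18 points depending on the cell. Describing the inequality as *greater than* is wrong on either reading of the parenthesis.

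This rests on exact binomial sampling with the Table 11-7 counts applied as fixed rules. The agreement of column (a) with the same rules supports that assumption.

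Two stronger inferences should be resisted. The table does not show faulty simulation or wrong cut-offs, since every printed cell in both columns reproduces. Nor is any result of the trial affected: SAP section 3 records that the expansion part was not started, so these operating characteristics were never used. The importance is low.

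**What to change.** Relabel column (b), in the text of section 11.8.2 and in the title of Table 11-8, as the probability that this stage's interim look is passed and the observed ORR is at least p1, with a note that each stage uses its own look only. The printed numbers can then stay. The alternative is to keep the caption and replace the p1 rows with the conditional, strict values in the table under working, recomputing the p0 rows in the same way.

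If cumulative figures over all looks are wanted, restate columns (a) and (b) together, because changing (b) alone would put two definitions side by side. For CRC at 15%, the chance of having stopped by each look would be 19.7/26.5/30.4%, and the chance of completing the stage at or above p1 would be 56.0/49.9/47.1%.

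The cost is a caption edit, or one recomputed column (two for the cumulative version). Neither the design nor the continuation counts change.
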